4.8.5. Vital Signs and Physical Examinations

Vital signs include: Height (cm), Weight (kg), Body Mass Index, Systolic Blood Pressure (mmHg), Diastolic Blood Pressure (mmHg) and Heart Rate (beats/min).

Height is assessed at Screening; Weight is assessed at Screening, Month 6 and Month 6 of the follow-up period. Other Vital Signs are assessed at Screening, Day 1, every month during the treatment period and at Months 1 and 3 from the follow-up period.

Physical Examination is assessed at Screening, Months 3 and 6 of treatment and follow-up periods.

The actual value and change from Baseline to each on study evaluation will be summarized by treatment group and overall for vital signs.

By-subject listings of vital sign measurements will be presented in data listings.

Physical examination results at each time point will be summarized by treatment group and overall; shifts from Baseline in physical examination findings to each on study visit will also be presented. All physical examination findings will be presented in a data listing.

4.8.6. Electrocardiogram

Local 12-lead ECG readings of QTcF are performed at Screening, Day 1 (pre and post-dose) and every month from the treatment period, as well as Months 1,3,6 from the follow-up period.

Baseline will be defined as the highest value prior to first dose.

Actual values and changes from baseline of ECG results will be summarized descriptively, as well as the number and percent of subjects with normal, abnormal and clinically significant abnormal results at Baseline and each study visit by treatment group and overall.

All ECG data for each subject will be provided in data listings.

Sponsor:	ObsEva		
Protocol:	18-OBE2109-002		
Document Version No.:	1.0	Document Date:	18-MAY-2021

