#### **Discontinuation Rules during the Treatment Period:**

Endometrial biopsies: in case of endometrial biopsy diagnosis being an endometrial hyperplasia of any type or worse, the subject will have to discontinue the treatment (and will not be eligible to enter the extension study) and will be advised to consult for a gynecological evaluation and treatment.

Serum calcium: Subjects who have a serum calcium level on treatment above 2.9 mmol/L should have calcium supplements interrupted. If serum calcium level on treatment is above 3.1 mmol/L calcium supplements **and study treatment** are to be interrupted. A repeat test of this parameter within 2 weeks

under fasting conditions is to be performed. If the results of the repeat remain above 2.9 mmol/L, study treatment should definitively be discontinued and the subject should be advised to consult an endocrinologist for further evaluation.

Bone mineral density loss: subjects who experience more than 8% BMD loss or a Z-score  $\leq -2.5$  at any site (femoral neck, hip or spine) will be discontinued from study treatment and will enter the follow-up period (they will not be eligible to enter the extension study).

Liver function tests: following the Food and Drug Administration (FDA) guidance on drug-induced liver injury (17), subjects who have an elevation of hepatic enzymes are to be withdrawn immediately from treatment if:

- ALT or AST  $>8\times\text{ULN}$
- ALT or AST  $>5\times\text{ULN}$  for more than 2 weeks
- ALT or AST  $>3\times\text{ULN}$  and (TBL  $>2\times\text{ULN}$  or INR  $>1.5$ )
- ALT or AST  $>3\times\text{ULN}$  with the appearance of fatigue, nausea, vomiting, right upper quadrant pain or tenderness, fever, rash, and/or eosinophilia ( $>5\%$ )

Withdrawn subjects will be followed up until hepatic parameters return to normal.

ECG : subjects who have a QTcF  $> 500$  ms or increase  $> 60$  ms from the highest value prior to first dose will have to be withdrawn from study treatment and followed up until return to QTcF  $< 480$  ms or – if not reached after 3 months of treatment cessation- be referred to a cardiologist.

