## Appendix A. Schedule of study assessments – Screening and Treatment Periods

Schedule of study assessments – Screening and Treatment Periods								
Timing 	Screening Period (up to 3 months  )	Treatment Period						
		Day 1	M1	M2	M3	M4	M5	M6
Informed Consent	x							
Inclusion-Exclusion criteria	x	x						
Demography, height, weight, medical history	x							x 
mB&B	x							
Columbia-Suicide Severity Rating Scale	x	x	x	x	x	x	x	x

 All post-baseline visits should take place at the end of the defined period (i.e. M1 visit should be scheduled at the end of Month 1, M2 visit should be scheduled at the end of Month 2, etc.). Post-baseline visits dates are calculated from Day 1 visit date. A month is defined as 28 days/4 weeks. Visits should be scheduled ± 3 days from the calculated date.

 If required for washout of oral contraceptives, other sex hormones, or GnRH antagonists/agonists (provided that the reason for discontinuing the previous GnRH-antagonist is not lack of efficacy), a period of up to 3 months is allowed between signing the informed consent and the screening visit.

 Only weight will be recorded.

Schedule of study assessments – Screening and Treatment Periods								
Timing 	Screening Period (up to 3 months  )	Treatment Period						
		Day 1	M1	M2	M3	M4	M5	M6
ECG	x	x 	x	x	x	x	x	x
Physical examination	x				x			x
Vital signs	x	x	x	x	x	x	x	x
Urine pregnancy test	x	x	x	x	x	x	x	x
TVUS of uterus	x				x			x
Gynecological examination	x				x			x
Endometrial biopsy	x							x 
Pap smear test	x							
Breast examination (mammogram if required)	x							x

 ECG on Day 1 should be performed twice: once before treatment and once after treatment (just before PK sampling).

 If endometrium thickness in TVUS is ≤ 5 mm, no endometrial biopsy will be necessary.

Schedule of study assessments – Screening and Treatment Periods								
Timing 	Screening Period (up to 3 months  )	Treatment Period						
		Day 1	M1	M2	M3	M4	M5	M6
Clinical laboratory & urinary protein dipstick	x	x 	x 	x	x 	x	x	x 
Blood sample for PK 		x	x	x	x	x	x	x
BMD by DXA	x							x
Adverse events	x	x	x	x	x	x	x	x
Previous/concomitant medication	x	x	x	x	x	x	x	x
Contraceptive dispensing and counselling	x	x	x	x	x	x	x	x

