1.2. Objectives of Statistical Analysis

Following the early termination of the study and due to the number of subjects randomized being substantially lower than the target number if the study had been fully enrolled, this statistical analysis plan (SAP) is focused on the safety analysis and all safety and efficacy data will be presented in listings. Consequently, this SAP is designed to outline the methods to be used in the analysis of study data to answer the safety and tolerability objectives.

The primary objective of this study was to demonstrate the efficacy and safety of linzagolix administered orally once daily for up to 3 months at a dose of 75 mg alone or of 200 mg in combination with ABT (E2 1 mg / NETA 0.5 mg) versus placebo, while under randomized treatment, in the management of moderate to severe EAP in women with surgically confirmed endometriosis. The two co-primary efficacy endpoints were clinically meaningful reduction over the last 28 days of randomized treatment up to the Month 3 visit along with a stable or decreased use of analgesics for EAP for 1) DYS and for 2) NMPP.

Secondary objectives included evaluation of persistence of efficacy over the last 28 days of randomized treatment up to the Month 6 visit, evaluation of pain associated with sexual intercourse (dyspareunia) and defecation (dyschezia), difficulty of doing daily activities, analgesic use, assessment of subject perception of severity, change in uterine bleeding, Quality of Life (QoL) questionnaires, pharmacoeconomic burden of endometriosis by assessing changes in patient productivity, assessment of endometriosis related number of non-study health visits, number of days in hospital and type of medical procedures performed during the Treatment Period.

Safety and tolerability objectives included assessment of BMD, endometrial health, cardiac safety including QT interval prolongation, standard laboratory safety parameters, gynecological assessments and AE frequency including specific hypoestrogenic AEs.

Exploratory objectives included assessment of bone turnover markers and collection of PK and PD data of linzagolix for a separate modelling exercise.

Populations for analysis, data handling rules, statistical methods, and formats for data presentation are provided. The statistical analyses and summary tabulations described in this SAP will provide the basis for the results sections of the clinical study report (CSR) for this trial.

Statistical Analysis Plan

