Bone mineral density loss: subjects who experienced more than 8% BMD loss or a Z-score ≤ -2.5 at any site (femoral neck, hip or spine) were to be discontinued from study treatment and were to enter the follow-up period (they were not eligible to enter the extension study).

Liver function tests: following the Food and Drug Administration (FDA) guidance on drug-induced liver injury, subjects who had an elevation of hepatic enzymes were to be withdrawn immediately from treatment if:

- ALT or AST >8 xULN
- ALT or AST >5 xULN for more than 2 weeks
- ALT or AST >3 xULN and (TBL >2 xULN or INR >1.5)

Sponsor:	ObsEva		
Protocol:	18-OBE2109-002		
Document Version No.:	1.0	Document Date:	18-MAY-2021

- ALT or AST >3xULN with the appearance of fatigue, nausea, vomiting, right upper quadrant pain or tenderness, fever, rash, and/or eosinophilia (>5%)

Withdrawn subjects were to be followed up until hepatic parameters returned to normal.

ECG : subjects with a QTcF > 500 ms or increase > 60 ms from the highest value prior to first dose were to be withdrawn from study treatment and followed up until return to QTcF < 480 ms or – if not reached after 3 months of treatment cessation- be referred to a cardiologist. They were to enter the 6-month Follow-Up Period and undergo follow-up ECGs according to the schedule of events.

2.3.2. **Unblinding**

The study design was double-blind for the subject, the clinical site and the operational team. The Sponsor was planned to be unblinded to active treatment groups, following the analysis of Month 6 visit data from the main study (18-OBE2109-002 - Edelweiss 2 study), but was to be blinded to the treatment allocated to patients who had previously received placebo.

A database lock was to be performed prior to unblinding of treatment.

Following the early termination of the studies (main and extension), the lock was to be performed at the same time for the main and extension studies, and the unblinding done for all subjects for both studies.

2.4. **Study Procedures**

Statistical Analysis Plan

Sponsor:	ObsEva		
Protocol:	18-OBE2109-002		
Document Version No.:	1.0	Document Date:	18-MAY-2021

The schedule of assessments, as outlined in the study protocol, is provided in Table 1 and Table 2.

Table 1 Schedule of Assessments – Screening and Treatment Periods

Schedule of study assessments – Screening and Treatment Periods							
Timing ¹	Screening Period (up to 3 months ²)	Treatment Period					
		Day 1	M1	M2	M3	M4	M5

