Baseline dysmenorrhea, non-menstrual pelvic pain, analgesic use and uterine bleeding will be based on the calculation from daily e-diary data from menstrual cycles during the screening period. The screening period must cover at least two full menstrual cycles. The following rules apply to select the two baseline menstrual cycles for assessment of eligibility and baseline:

- If only two full screening cycles are covered prior to Day 1: those two screening cycles should be used for both eligibility assessment and baseline calculation.
- If 3 full screening cycles are covered during the screening period, for logistical reasons, as allowed per protocol: "If for logistical reasons beyond her control, the subject is unable to come to the clinic for Day 1 within the acceptable time window (1st to 7th day inclusive of the cycle) then the subject will be allowed to start Day 1 in the following cycle (again on the 1st to 7th day of the cycle). In this case, the eligibility assessments should be assessed based on the first two cycles only"; the two first screening cycles should be used for both eligibility assessment and baseline calculation.
- If more than 3 full screening cycles are covered during the screening period: the two last menstrual cycles prior to the baseline visit will be considered for both eligibility assessment and baseline calculation.
- Due to possible technical issues with the e-diary device, some data during the screening menstrual cycle may not be collected properly. Consequently the menstrual cycles may not be considered as valid for assessment of eligibility and baseline and other cycles than first and second ones might be used on a case-by-case basis. The sponsor will provide an excel file listing all the menstrual cycles that were used for measurement of eligibility and baseline.

The baseline DXA assessment will be derived as the latest non-missing DXA assessment with acceptable quality (accepted="Yes") prior to the Baseline visit or the first non-missing assessment

Sponsor:	ObsEva		
Protocol:	18-OBE2109-002		
Document Version No.:	1.0	Document Date:	18-MAY-2021

with acceptable quality (accepted="Yes") done up to 10 days after the baseline visit if there is no assessment prior to baseline.

For other data not specified before, baseline will be defined as the data most recently collected prior to the first dose of IMP.

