4.5.1. Demographics

Demographics and baseline characteristics will be summarized by treatment group and overall using descriptive statistics.

Demographics and baseline data include Age (years), Gender, Ethnicity, Race, Height (cm), Weight (kg), Body Mass Index (kg/m²), Systolic Blood Pressure (mmHg), Diastolic Blood Pressure (mmHg), Heart Rate (beats/minute), QTc interval (Fridericia) (ms).

BMI is auto-calculated, defined as: Weight (kg)/(Height(m)*Height(m)).

Demographic and Baseline data will be provided in data listings.

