- Table 14.4.2.2 Hematology Parameters - Shifts from Baseline Based on Clinical Findings up to Month 6 Follow-up – Safety Analysis Set
- Table 14.4.2.3 Hematology Parameters - Shifts from Baseline Based on Normal Ranges up to Month 6 Follow-up – Safety Analysis Set
- Table 14.4.3.1 Coagulation Parameters by Visit up to Month 6 Follow-up – Safety Analysis Set
- Table 14.4.3.2 Coagulation Parameters - Shifts from Baseline Based on Clinical Findings up to Month 6 Follow-up – Safety Analysis Set
- Table 14.4.3.3 Coagulation Parameters - Shifts from Baseline Based on Normal Ranges up to Month 6 Follow-up – Safety Analysis Set
- Table 14.4.4.1 Chemistry Parameters by Visit up to Month 6 Follow-up – Safety Analysis Set
- Table 14.4.4.2 Chemistry Parameters - Shifts from Baseline on Clinical Findings up to Month 6 Follow-up – Safety Analysis Set
- Table 14.4.4.3 Chemistry Parameters - Shifts from Baseline on Reference Ranges up to Month 6 Follow-up – Safety Analysis Set
- Table 14.4.5.1 Lipids by Visit up to Month 6 Follow-up – Safety Analysis Set
- Table 14.4.5.2 Lipids - LDL and HDL Categories by Visit up to Month 6 Follow-up – Safety Analysis Set
- Table 14.4.5.3 Lipids - Shifts from Baseline Based on LDL Categories up to Month 6 Follow-up – Safety Analysis Set
- Table 14.4.5.4 Lipids - Shifts from Baseline Based on Triglycerides Categories up to 6 Month Follow-up – Safety Analysis Set
- Table 14.4.5.5 Lipids Parameters - Shifts from Baseline Based on Clinical Findings up to 6 Month Follow-up – Safety Analysis Set

Sponsor:	ObsEva		
Protocol:	18-OBE2109-002		
Document Version No.:	1.0	Document Date:	18-MAY-2021

- Table 14.4.5.6 Lipids Parameters - Shifts from Baseline Based on Normal Ranges from up to 6 Month Follow-up –Safety Analysis Set
- Table 14.4.6.1 Serum levels of E2, P4, SHGB and LH up to Month 6 Follow-up – Safety Analysis Set
- Table 14.4.6.2 Estradiol [E2] Categories by Visit up to 6 Month Follow-up – Safety Analysis Set
- Table 14.4.6.3 Proportions of Subjects with P4 at Least once >10.0 nMol/L from Study Day 1 to Month 6 – Safety Analysis Set
- Table 14.4.7.1 Vital Signs by Visit up to Month 6 Follow-up– Safety Analysis Set
- Table 14.4.8.1 Physical Examination Findings up to Month 6 Follow-up– Safety Analysis Set
- Table 14.4.8.2 Physical Examination Findings - Shifts from Baseline up to Month 6 Follow-up – Safety Analysis Set
- Table 14.4.9.1 ECG - QTcF by Visit up to Month 6 Follow-up – Safety Analysis Set

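### SAP 4.8.6 takes the highest pre-dose ECG value as baseline for mean QTcF change, which pushes the within-arm and overall mean changes downward

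*SAP*

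**What the plan says.** SAP 4.8.6 (Electrocardiogram) defines the ECG baseline: "Baseline will be defined as the highest value prior to first dose". It then plans descriptive summaries of actual values and changes from baseline, by treatment group and overall. SAP 4.2.1 includes the mean among the statistics for change from baseline. The output concerned is Table 14.4.9.1, "ECG - QTcF by Visit up to Month 6 Follow-up".

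SAP 4.8.6 and Protocol Appendix A (with footnote 4) schedule two pre-dose ECGs, one at Screening and one on Day 1 before dosing. After the first dose there is one ECG later on Day 1 and one at each visit that has an ECG.

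The highest pre-dose value appears elsewhere only as the reference for an individual criterion. In Protocol 10.7.2.1, subjects whose QTcF rises by more than 60 ms "from the highest value prior to first dose will have to be withdrawn from study treatment". SAP 2.3.1 repeats the rule.

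The SAP's general default is different. Under SAP 4.2.11, for data with no specific rule, "baseline will be defined as the data most recently collected prior to the first dose of IMP". SAP 4.8.6 gives no reason for departing from this, and SAP section 5 does not list it as a change.

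**The concern.** The baseline is a maximum of two readings and each follow-up value is a single reading. The maximum is selected partly because its measurement error is positive, and the later reading is not selected in this way. The mean change is therefore below zero under no drug effect, and below the true effect when there is one. The error is in the reassuring direction.

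The SAP names "cardiac safety including QT interval prolongation" among its safety objectives. Protocol 5.5.1 reports a borderline QTc effect in a dedicated study, above its limit of concern by less than 2 ms, and Protocol 5.7 mentions that finding when it commits to monthly ECGs. An offset of several milliseconds in the mean-change column is large on that scale.

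Neither planned ECG table (14.4.9.1 or 14.4.9.2) is described as counting subjects by size of QTcF increase, so no planned table needs the highest value as its reference.

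**Working it through.** The documents state no expected QTcF change, so there is no plan figure to reproduce.

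**Inputs from the documents**
- Pre-dose readings per subject: 2 (SAP 4.8.6; Protocol Appendix A).
- Readings per later visit: 1.
- Entry limit: QTcF above 450 ms excludes at Screening or Day 1 pre-dose (Protocol 9.2.2, criterion 15).

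**Assumed inputs (not in the documents)**
- Within-subject SD *s*: 5 to 12 ms.
- True drug effect for illustration: +5 ms.
- For the simulation: population mean 405 ms, between-subject SD 15 ms, normal and independent errors.

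**Step 1: direction.** The maximum of the pre-dose values is never below the last value or the mean of the values. Each subject's change is therefore equal or lower under the highest-value rule, and the mean is lower whenever the two readings differ. This needs no distributional assumption.

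**Step 2: size without the entry limit.** The expected maximum of two independent standard normal errors is 1/√π = 0.564, so the shift in mean change is -0.564 × *s*. If the two pre-dose errors have correlation ρ, the shift is -*s* × √((1-ρ)/π); at ρ = 0.5 that is -0.399 × *s*.

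| *s* (ms) | Shift, independent errors (ms) | Shift, ρ = 0.5 (ms) |
|---|---|---|
| 5 | -2.8 | -2.0 |
| 6 | -3.4 | -2.4 |
| 8 | -4.5 | -3.2 |
| 10 | -5.6 | -4.0 |
| 12 | -6.8 | -4.8 |

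A third (unscheduled) pre-dose ECG raises the multiplier to 3/(2√π) = 0.846. A subject with only one pre-dose ECG has no shift.

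**Step 3: with the 450 ms entry limit.** Simulated mean change, placebo / active with a true effect of +5 ms, 4,000,000 subjects per SD:

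| *s* (ms) | Highest value | Last value | Mean of two |
|---|---|---|---|
| 5 | -2.81 / +2.19 | +0.01 / +5.01 | 0.00 / +5.00 |
| 6 | -3.36 / +1.64 | +0.01 / +5.01 | +0.02 / +5.02 |
| 8 | -4.46 / +0.54 | +0.03 / +5.03 | +0.03 / +5.03 |
| 10 | -5.52 / -0.52 | +0.08 / +5.08 | +0.08 / +5.08 |
| 12 | -6.52 / -1.52 | +0.17 / +5.17 | +0.17 / +5.17 |

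Active minus placebo is 5.00 ms in every cell.

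A second simulation moved the assumed mean to 410 or 420 ms, the between-subject SD to 12 or 18 ms and *s* to 5, 10 or 15 ms. With no drug effect, the highest-value rule gave -2.7 to -7.7 ms. The last or mean value gave 0.0 to +1.5 ms, the upper end arising where the entry limit truncates most.

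**Step 4: the overall column.** With equal arms, *s* = 8 and +5 ms in both active arms, the highest-value rule gives (-4.46 + 0.54 + 0.54)/3 = -1.1 ms. The last-value rule gives (0.03 + 5.03 + 5.03)/3 = +3.4 ms.

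**Step 5: spread of the change at *s* = 8, no entry limit.**
- Highest value: 8 × √(2 - 1/π) = 10.4 ms.
- Last value: 8 × √2 = 11.3 ms.
- Mean of two: 8 × √1.5 = 9.8 ms.

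**The case against.** The strongest point on the other side is that no comparative result changes. The shift has the same expectation in each randomized arm, the placebo column sits beside the active columns, and actual values and listings are reported as well. The analysis is descriptive, in a trial stopped early with far fewer subjects than planned, and no decision rests on mean QTcF change. The ECGs are local readings used mainly for individual monitoring, and the mean QTc question was addressed in a dedicated study with placebo and a positive control. The highest-value rule also keeps one ECG reference across the individual criterion and the summaries. Finally, both the within-subject SD and the +5 ms effect are assumed: with independent errors the active mean turns negative only from an SD of about 10 ms, and at correlation 0.5 it stays positive throughout the range shown.

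Most of this stands, and it limits the point to within-arm and overall means. It does not justify the rule. The individual criterion can keep its own reference without passing it to group means. SAP 4.8.6 plans no active-minus-placebo figure, so the cancellation is left to the reader, and it does not help the pooled overall column. Even where the active mean stays positive, it is understated by the full shift.

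**Conclusion.** The concern holds and should be fixed. As written, SAP 4.8.6 lowers the within-arm and overall mean QTcF change relative to a last-value or mean-value baseline. The direction is certain whenever pre-dose readings differ.

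The size depends on the unstated within-subject SD: -2.8 to -6.8 ms for SDs of 5 to 12 ms with independent errors, and -2.0 to -4.8 ms if the pre-dose errors correlate at 0.5. These figures take two pre-dose readings per subject and leave out the entry limit, which reduces the shift slightly. The expected difference between arms, the post-baseline actual values and the listed readings are not affected.

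**What to change.** - In SAP 4.8.6, define baseline for the QTcF change summaries as either the last pre-dose value (already the default in SAP 4.2.11) or the mean of the pre-dose values, and say which. Either removes the shift, apart from the small entry-limit effect shown above. The last value needs no new definition; the mean gives the smaller SD of change.
- Use the same value for the baseline QTcF in SAP 4.5.1.
- Keep the highest pre-dose value only as the reference for listing subjects against the protocol's individual QTcF criterion, which stays unchanged.
- Optionally, add the descriptive active-minus-placebo difference in mean change to Table 14.4.9.1. The correction does not depend on it.

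The cost is one line of SAP text, a baseline flag and, if wanted, the added difference in one table. No new data are needed. Reported within-arm changes may look slightly less favourable. Choosing the last value raises the SD of change somewhat compared with the present rule.
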